6.3 Justification of selection criteria

The selection criteria are chosen to ensure that patients with specific risks for administration of the study drugs and / or patients with conditions which may have an impact on the aims of the study are excluded.

6.4 Withdrawal of patients from study

6.4.1 Withdrawal

6.4.1.1 Screening failure

Depending on the time point of withdrawal before receiving study treatment, a withdrawn patient is referred to as either "FGFR testing failure" (those that are FGFR testing) or "screening failure" as specified below:

FGFR testing failure

A patient who was tested for FGFR mRNA expression level by FGFR1/3 RNAscope *in situ* hybridization assay and the test result for FGFR1 or 3 mRNA expression levels was not RNAscope score of 3+ or 4+ (measurement is part of this protocol) or fails to satisfy the selection criteria **must not** be screened for study treatment eligibility but **needs to be**

23 MAY 2023 Version 6.0 Page: 47 of 181

withdrawn from the study and is regarded a "FGFR testing failure". The "FGFR testing failure" will be registered.

Re-testing is allowed if an unevaluable test result occurs.

See Section 11.1 for data to be collected for FGFR testing failures (those that are FGFR test negative and/or those that do not meet the inclusion/exclusion criteria for FGFR testing).

Screening failure

A patient who, for any reason (e.g. failure to satisfy the selection criteria), terminates the study before start of study treatment is regarded a "screening failure".

See Section 11.1 for data to be collected for screening failures.

6.4.1.2 Re-screening

Re-testing for FGFR expression level after obtaining an initial negative result is not allowed.

Re-starting the defined set of screening procedures to enable the "screening failure" patient's participation at a later time point is **not** allowed.

Re-screening might be possible considering the following examples:

- The patient had successfully passed the screening procedures, but could not start subsequent treatment on schedule.
- Initial screening occurred too early to complete the required washout period after prior therapy.
- The inclusion / exclusion criteria preventing the patient's initial attempt to participate have been changed (via protocol amendment).

Re-screening of patients who have failed screening may only be allowed **once** after discussion with the sponsor's designated medical representative and after approval by the sponsor. Sponsor approval of re-screening for a patient must be documented.

In any case, the investigator has to ensure that the repeated screening procedures do not expose the patient to an unjustifiable health risk. Also, for re-screening, the patient has to resign the informed consent form, even if it was not changed after the patient's previous screening.

The screening failure will be registered to close the patient identification number (PID), and re-screening will start again by signing a new informed consent form and being assigned a new PID.

6.4.1.3 Withdrawal criteria

Patients *must* be withdrawn from the study treatment if any of the following occurs:

• Consent withdrawal at their own request or at the request of their legally acceptable

23 MAY 2023 Version 6.0 Page: 48 of 181

representative.

o At any time during the study and without giving reasons, a patient may decline to participate further. The patient will not suffer any disadvantage as a result.

• Substantial non-compliance with study procedures

- Patients requiring a dose interruption of rogaratinib due to toxicity > 21 days from the next intended dose or due to other reasons for > 31 days from the next intended dose will be withdrawn from the study treatment.
- o Off study drug (atezolizumab) longer than 42 days from the next intended dose
 - If, in the judgment of the investigator, the patient is likely to derive clinical benefit from resuming atezolizumab after a hold > 42 days, atezolizumab may be restarted after sponsor approval.
 - If patients must be tapered off steroids used to treat adverse events, atezolizumab may be held for > 42 days. The acceptable length of interruption will depend on agreement between the investigator and the sponsor. (See also Section 7.4.3.3 for further details and specific recommendations).
- Lost to follow-up
- o Use of another non-protocol anti-cancer therapy

• Unacceptable toxicity

- If, in the investigator's opinion, continuation of study would be harmful to the patient's well-being.
- Any toxicity requiring rogaratinib dose reductions below dose level -2.
- Any toxicity requiring rogaratinib dose interruption longer than 21 days to resolve to Grade 1 or better.
- Severe (Grade 3 or higher) allergic reactions such as exfoliative erythroderma, anaphylaxis, or vascular collapse.
- o Severe (Grade 3 or higher) infusion-related reactions.
- Any other potential adverse reaction deemed sufficiently serious to warrant discontinuation of treatment by the investigator or his designated associate(s).
- O Any decrease in visual acuity, ocular pain or discomfort, or symptomatic retinal disorders including retinal detachment / retinal pigment epithelial detachment / central serous retinopathy / retinal vein occlusion classified analog to CTCAE v.4.03 as Grade 2 or higher. Based on the individual benefit risk assessment and after discussion with the sponsor, patient may interrupt treatment until recovery to at least Grade 1 and then treatment may be resumed at one dose level below. Patients with low visual acuity at baseline (best corrected visual acuity worse than 20/40 and up to 20/200) have to undergo individual clinical evaluation to determine the maintenance in the study, according to investigator's judgement and based on the individual benefit risk

23 MAY 2023 Version 6.0 Page: 49 of 181

assessment.

- o Liver toxicity with AST or ALT > 3 x ULN with concomitant bilirubin > 2 x ULN in the absence of an alternative explanation for these elevations.
- \circ \geq Grade 3 liver toxicity with ALT or AST > 5 x ULN and/or total bilirubin > 3 x ULN in the absence of an alternative explanation for these elevations.
- Any grade myasthenic syndrome/myasthenia gravis, Guillain-Barré or meningoencephalitis.
- o Any grade of recurrent symptomatic pancreatitis.
- o Newly diagnosed soft tissue mineralization suspected to be caused by rogaratinib.
- o Grade 4 non-hematological toxicity (laboratory abnormalities of any grade will not be considered toxicity unless deemed clinically significant by the investigator).
- o Grade 3 or higher non hematologic toxicity atezolizumab-related and requiring treatment discontinuation (see also Section 7.4.3.3).
- Any Grade 2 or higher non hematologic toxicity atezolizumab-related not resolving at Grade 1 or better within 12 weeks despite symptomatic therapy
- Pregnancy as confirmed by a positive serum beta-HCG test. Pregnancy will be reported under the same timelines as a serious adverse event.
- At specific request of the sponsor.

Patients may be withdrawn from the study treatment if any of the following occurs:

- If the patient develops conditions which would have prevented his/her entry into the study according to the inclusion / exclusion criteria, he/she must be withdrawn immediately if safety is concerned; in other cases, the investigator will decide whether there is a conflict for the patient to continue.
- Development of a second malignancy that requires a different treatment. At investigator's discretion study treatment may continue if UC has a poorer prognosis as compared with the second malignancy of new onset.
- Development of any intercurrent illness or situation which may, in the judgment of the investigator, affect assessments of clinical status and study endpoints to a relevant degree.
- Use of illicit drugs or other substances that may, in the opinion of the investigator or his designated associate(s), have a reasonable chance of contributing to toxicity or otherwise confound the results.
- Symptomatic deterioration (i.e. uncontrollable pain secondary to disease or unmanageable ascites, etc.) attributed to disease progression as determined by the investigator after integrated assessment of radiographic data and clinical status.

23 MAY 2023 Version 6.0 Page: 50 of 181

- Disease progression per RECIST v1.1. At discretion of the investigator, willing patients will be permitted to continue study treatment after radiologic progression according to RECIST v1.1 if all the following criteria are met:
 - Evidence of clinical benefit (defined as the stabilization or improvement of disease-related symptoms) as assessed by the investigator.
 - Absence of symptoms and signs indicating unequivocal progression of disease (including worsening of laboratory values [e.g. new or worsening hypercalcemia]).
 - o No decline in ECOG performance status that can be attributed to disease progression.
 - Absence of tumor progression at critical anatomical sites (e.g. leptomeningeal disease) that cannot be managed by protocol-allowed medical interventions.

In addition, treatment beyond progression should not delay an imminent intervention to prevent serious complications of disease progression (e.g. central nervous system [CNS] metastases).

Patients for whom radiographic disease progression is confirmed at a subsequent tumor assessment may be considered for continuing study treatment at the discretion of the investigator if they still meet the criteria above and in absence of unacceptable toxicity.

For patients who withdraw consent to study, no further study-related procedures will be allowed. The patient will not suffer any disadvantage as a result. Any patient removed from the study will remain under medical supervision until discharge or transfer is medically acceptable.

After permanent treatment discontinuation, a safety assessment visit must be scheduled for all patients (refer to Section 5.2.3). After primary completion, follow-up information will not be collected after safety assessment visit.

Withdrawal from active follow-up

Patients *must* be withdrawn from active follow-up if any of the following occurs:

- Radiologically confirmed PD of urothelial carcinoma is observed (investigator assessment). (*Note*: this applies only to the further efficacy assessments during the active follow-up period in patients who prematurely discontinued study treatment for reasons other than radiological disease progression).
- Start of subsequent systemic anti-cancer treatment. (Note: this applies only to the further efficacy assessments during the active follow-up period in patients who prematurely discontinued study treatment for reasons other than radiological disease progression).
- At their own request or at the request of their legally acceptable representative. At any time during the study and without giving reasons, a patient may decline to participate further. The patient will not suffer any disadvantage as a result.
- Development of a malignancy other than urothelial carcinoma
- Substantial non-compliance with the requirements of the study

23 MAY 2023 Version 6.0 Page: 51 of 181

- Withdrawal of consent to active follow-up visits
- If, in the investigator's opinion, continuation of the active follow-up visits would be harmful to the patient's well-being
- Patient lost to follow-up
- Death

Withdrawal from long-term follow-up

Patients *must* be withdrawn from long-term follow-up if any of the following occurs:

- Withdrawal of consent to long-term follow-up
- Patient lost to follow-up
- Death

Patients lost to follow-up

If a patient is lost to follow-up at any stage of the study, the site will try to contact the patient, the patient's relatives, or another doctor treating the patient, unless prohibited by local requirements. All attempts to contact the patient or relatives should be documented and sites are expected to make at least 5 attempts to contact the patient over the course of 3 months. An additional contact attempt should be made at the time of the survival sweep.

6.4.1.4 General procedures

In all cases, the reason for withdrawal must be recorded in the eCRF and in the patient's medical records. See Section 11.1 for data recoding.

The patient may object to the generation and processing of post-withdrawal data as specified in Section 13.4.

Details for the premature termination of the study as a whole (or components thereof) are provided in Section 12 (Premature termination of the study).

6.4.2 Replacement

Replacement of patients may occur in Part A in order to ensure the necessary number of evaluable patients for dose selection (at least 4 patients per tested dose level, a total of 20 evaluable patients). Patients who are not valid for efficacy assessment may be replaced, to ensure at least 26 valid patients for assessment of the RP2D. Patients may be replaced in the following circumstances:

Dose selection:

• Patients who discontinue or took less than 80% of the per protocol required total dose of either study drug (rogaratinib or atezolizumab) during the first cycle due to any reason

23 MAY 2023 Version 6.0 Page: 52 of 181

other than a DLT (note: protocol-defined dose reductions will not be considered incompliant).

Efficacy:

• Patients who took less than 80% of the per protocol required total dose of either study drug (rogaratinib or atezolizumab) during the first two cycles or patients without an efficacy assessment.

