10.2 Analysis sets

Safety analysis set (SAF)

All patients who received at least 1 dose of study drug and have post-treatment safety data available will be included in the safety evaluation.

MTD analysis set

All patients who completed Cycle 1 and who took at least 80% of the required total dose (protocol-defined dose reductions will not be considered incompliant) of either study drug (rogaratinib or atezolizumab) during Cycle 1 or discontinued during Cycle 1 due to a DLT will be included in the MTD evaluation.

Efficacy analysis set

All patients who have received at least 1 dose of study drug and who have post-baseline efficacy data available will be included in the efficacy evaluation.

Pharmacokinetics (PK) analysis set (PKS)

All patients who have received at least 1 dose of study drug and with at least 1 valid concentration after first dosing and no important protocol deviations affecting the validity will be included in the PK evaluation.

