10.4 Determination of sample size

This Part A of the study is primarily a descriptive safety and tolerability Phase 1b trial.

No formal sample size calculation has been done for the dose selection part due to the exploratory nature of this Part A of the study. It is expected that up to 20 evaluable patients will be enrolled for safety and for the dose selection part. After 20 patients included in the dose selection, enrollment will continue up to a total of 26-30 patients at the most promising dose with regard to safety and efficacy to obtain additional data on safety, PK, and clinical activity.

A sample size of at least 26 evaluable patients at the MTD/RP2D will lead to a Bayesian posterior probability $P(\pi \le 0.4 \mid data)$ of at least 91% with a power of at least 96% and a Bayesian posterior probability $P(\pi > 0.4 \mid data)$ of at least 92% and with 80% power assuming a true population proportion for the response rate of π_u =0.6 under the alternative hypothesis for the upper criteria and a population proportion of π_l =0.15 under the alternative hypothesis for the lower criteria.

In case that the highest dose of rogaratinib (800 mg b.i.d.) is well tolerated in combination with atezolizumab, it is expected that the minimum of 26-30 evaluable patients is included. Assuming a dropout rate of 15%, a total minimum sample size of approximately 30 patients at the MTD/RP2D is expected.

Based on tolerability, different rogaratinib starting doses may be explored in this study. And in addition to FGFR testing, tumor tissue will be tested for further potential predictors of response (e.g. PIK3CA mutations). If, for example, the most promising rogaratinib dose or patient subgroups are not clearly defined, approximately 20 additional patients may be enrolled up to a total of 50 patients to confirm signals in a larger sample size, when rogaratinib in combination with atezolizumab seems to be tolerated and early signs of clinical activity have been observed. This decision will be made by the Sponsor after consultation with the investigators.

All calculations were performed with SAS 9.4 using non-informative Jeffrey's priors.

23 MAY 2023 Version 6.0 Page: 142 of 181

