4.2 Handling of Dropouts

Pre-screening failure = Subject signed ICF for FGFR testing but, for any reason, did not sign the ICF for study treatment eligibility.

Screening failure = Subject signed ICF for study treatment eligibility but, for any reason (e.g. failure to satisfy the selection criteria), terminated the study before start of study treatment.

Dropout = Subject discontinued study participation prematurely for any reason after start of study treatment. The start of the treatment period is defined by the first administration of study treatment.

Replacement of subjects may occur in Part A in order to ensure the necessary number of evaluable subjects for dose selection (at least 4 subjects per tested dose level, a total of 20 evaluable subjects) and to ensure at least 26 valid subjects for assessment of the RP2D. Subjects maybe replaced in the following circumstances:

Dose selection:

- Subjects who discontinue or took less than 80% of the per protocol required total dose of either study drug (rogaratinib or atezolizumab) during the first cycle due to any reason other than a DLT (*note*: protocol-defined dose reductions will not be considered incompliant).

Efficacy:

- Subjects who took less than 80% of the per protocol required total dose of either study drug (rogaratinib or atezolizumab) during the first two cycles or subjects without an efficacy assessment.

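### The 26 patients named for assessing the RP2D are counted under a dose rule with no toxicity exception, and that count matches no analysis set

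*Protocol*

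**What the plan says.** Protocol 6.4.2 sets two replacement rules side by side, and SAP 4.2 repeats both.

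- **Dose selection.** A patient may be replaced for discontinuing, or for taking under 80% of either drug, "during the first cycle due to any reason other than a DLT" (SAP 4.2). A note adds that "protocol-defined dose reductions will not be considered incompliant".
- **Efficacy.** A patient may be replaced who "took less than 80% of the per protocol required total dose of either study drug (rogaratinib or atezolizumab) during the first two cycles", or who has no efficacy assessment. Neither the DLT exception nor the reduction note appears here.

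The efficacy rule has a stated purpose: "Patients who are not valid for efficacy assessment may be replaced, to ensure at least 26 valid patients for assessment of the RP2D". SAP 4.2 gives the same aim, "to ensure at least 26 valid subjects for assessment of the RP2D". Protocol 10.4 builds its operating characteristics on "A sample size of at least 26 evaluable patients at the MTD/RP2D". Protocol 5.1 says the 26 to 30 evaluable patients supply further safety data to confirm the MTD and determine the RP2D. Beyond the replacement rule itself, neither document defines valid or evaluable for this count.

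The efficacy analysis set (Protocol 10.2, SAP 5.1) is "All patients who have received at least 1 dose of study drug and who have post-baseline efficacy data available", with no dose threshold. The ORR definition (Protocol 10.3.3.1, SAP 6.2.2) treats patients without any efficacy assessment as non-responders.

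**The concern.** Whether a dose can be recommended depends partly on how many patients cannot stay on it. A count that names its members as those valid for assessing the RP2D, yet lets toxicity-related under-dosing make a patient replaceable, leaves open whether those patients belong to that assessment. A patient who stops in Cycle 1 for a DLT is kept for dose selection by one rule and made replaceable by the next.

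There is a second, separate gap. The number 26 has at least two possible meanings: patients meeting the dose rule, or patients in the efficacy set. The efficacy set in turn leaves out patients whom the ORR definition explicitly counts. Depending on which denominator is used, the same data give different response rates.

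**Working it through.** **1. The plan's own figures (Protocol 10.4).** With a Jeffreys prior, the posterior after x responders in n is Beta(0.5 + x, 0.5 + n − x). For n = 26:

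- Upper criterion: x = 14 gives P(π>0.4) = 0.924 (x = 13 gives 0.851). The chance of 14 or more at π = 0.6 is 0.801.
- Lower criterion: x = 7 gives P(π≤0.4) = 0.916 (x = 8 gives 0.831). The chance of 7 or fewer at π = 0.15 is 0.968.

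These reproduce the stated 92% with 80% power and 91% with 96% power.

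**2. When toxicity makes a patient replaceable.**

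- Atezolizumab: two infusions fall in Cycles 1 and 2, and the dose is never reduced (7.4.3.3). One withheld gives 1/2 = 50%. Being unable to start Cycle 2 because of toxicity is itself a listed DLT (7.4.3.1).
- Rogaratinib at 800 mg b.i.d.: 84 doses × 800 = 67,200 mg, and 80% of that is 53,760 mg. The allowed shortfall is 13,440 mg, or 13,440/1,600 = 8.4 days. A 9-day hold gives 66/84 = 78.6%. After a DLT, 7.4.3.2 permits a delay of up to 21 days.
- Hold plus reduction: a hold on Days 15–21 followed by 600 mg b.i.d. gives 28×800 + 42×600 = 47,600 mg. Against 67,200 mg that is 70.8%. If the required dose is taken after the reduction (42×800 + 42×600 = 58,800 mg), it is 81.0%. Here the missing note decides the outcome.
- Reduction alone: Cycle 2 at 600 mg b.i.d. with nothing missed gives 58,800/67,200 = 87.5%, so it does not trigger the rule.

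**3. The sets side by side**, taking no efficacy assessment and no post-baseline efficacy data to mean the same thing:

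| Treated patient | Count of 26 | SAF | Efficacy set | ORR definition |
|---|---|---|---|---|
| At least 80% of both drugs, assessed | counted | in | in | by response |
| Under 80% through toxicity, assessed | replaceable | in | in | by response |
| Not assessed | replaceable | in, if safety data exist | out | non-responder |

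No column agrees with the count of 26, and the last two columns disagree on the last row.

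**4. Effect on a result at the cut-off.** Suppose 14 of 26 valid patients respond:

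- 14/26 = 53.8%, P(π>0.4) = 0.924
- two replaced non-responders added: 14/28 = 50.0%, 0.860
- four added: 14/30 = 46.7%, 0.773
- two added, one a responder: 15/28 = 53.6%, 0.927

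For unassessed patients, non-response is not an assumption, because the ORR definition imposes it. For under-dosed patients with scans it is an assumption.

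**5. Range under assumed response rates.** The documents give no response rate for under-dosed patients. Assume 0.6 in those who tolerate two cycles and 0.2 in the rest. With 10%, 15%, 20% or 30% in the second group, the all-treated ORR is 0.56, 0.54, 0.52 or 0.48. The chance of at least 14/26 is then 0.66, 0.59, 0.50 or 0.34, against 0.80 if only tolerant patients are counted. If both groups respond alike, the difference is zero.

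**The case against.** A reader might infer that the rule drops intolerant patients, so that the RP2D assessment is conditioned on tolerance and intolerance would read as none out of 26. The documents do not support that. Replacement is optional and adds a patient. No analysis set uses the two-cycle dose threshold. The SAF keeps every treated patient with safety data, the MTD set keeps those who discontinued in Cycle 1 for a DLT, and the efficacy set keeps anyone with post-baseline efficacy data. RP2D decisions draw on all available PK and safety data. SAP 6.4 and 6.4.2 summarise dose modifications and percent of planned dose, and list TEAEs leading to reduction, interruption and discontinuation. All of this stands.

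Further limits also stand:

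- The 92% is a sample-size property in 10.4. The SAP contains no posterior-probability analysis or go/no-go rule, and the study is exploratory.
- The required dose can be read as already allowing for reductions, which rescues some hold-and-reduce patients (step 2). It does not rescue a withheld infusion or a 9-day hold, because the note credits reductions, not holds.
- The 26 does not by itself close enrolment: the text says at least 26, then 26 to 30, with up to 50 in Part A.
- Four replaced patients cannot be inferred from the assumed 15% dropout, since SAP 4.2 defines dropout as leaving the study early, not under-dosing.

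Sound analysis sets still do not say who the 26 are, and the efficacy set itself disagrees with the ORR definition.

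**Conclusion.** The point holds as a mismatch of definitions. The efficacy replacement rule lacks the DLT exception and reduction note of its neighbour, so patients under-dosed through toxicity may be replaced in the count named for assessing the RP2D. That count corresponds to no analysis set, and the efficacy set omits patients whom the ORR definition counts as non-responders.

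Any bias arises only if the 26, or an efficacy set without unassessed patients, serves as the denominator. Its size cannot be derived from the documents. The fall from 0.924 to 0.860 or 0.773 shows only that a result at the cut-off can change; it assumes 14 responders among 26 and that every patient added back is a non-responder. The unassessed patients are the firmer part, because there the two definitions conflict whatever response rate is assumed.

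**What to change.** - In Protocol 6.4.2 and SAP 4.2, add to the efficacy rule the note that protocol-defined dose reductions are not non-compliance. This does not cover holds or withheld infusions, so the next item is also needed.
- State that every treated patient at the RP2D, replaced or not, stays in the RP2D assessment and in the ORR denominator, with unassessed patients as non-responders as 10.3.3.1 already says. Align the efficacy set in Protocol 10.2 and SAP 5.1 with this.
- State the 26 in 10.4 on that same set.
- Report replaced patients with reasons, and show the subset with at least 80% dose only as supportive.

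The cost is wording in two documents plus a short listing. The ORR may look slightly less favourable. If enrolment is already complete, the denominator statement, the aligned set and the listing can still be applied in reporting.
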